# 5.11 Medical Care of Subjects after End of Study

The Sponsor will not provide any additional care to subjects after they leave the study. Subjects will return to the care of their personal physician.

### 5.12 Treatment Compliance

It is the Investigator's responsibility to ensure that subjects are instructed in the proper use of study drug and that the subjects are fully compliant with their assigned dosage regimen, as well as the timing for taking the study drug relative to meals (see Section 5.8).

The prescribed dosage, timing, and mode of study drug administration may not be changed. Any departures from the intended regimen must be recorded in the eCRF.

At Day 14 and Day 42, previously dispensed study drug will be retrieved by the Investigator and compliance assessed. Subjects will be asked to return all unused medication at each visit.

Adequate compliance is defined as taking between 80% and 120% of dispensed study drug. Compliance problems (e.g., missing 2 or more consecutive full days [at least 6 doses] or taking less than 80% or more than 120% of the doses between study visits) should be discussed with the Medical Monitor to determine if the subject may continue in the study.

# 5.13 Study Drug Accountability

The Investigator, a member of the investigational staff, or a hospital pharmacist must maintain an adequate record of the receipt and distribution of all study drug using the Drug Accountability Form. These forms must be available for inspection at any time.

All study drug supplies should be accounted for at the termination of the study and a written explanation provided for discrepancies. All unused study drug supplies and packaging materials are to be inventoried and returned by the Investigator as instructed by the Sponsor. The study drug may be destroyed at the site with the consent of the Sponsor.

# 6.0 EFFICACY, PHARMACOKINETIC, SAFETY, HEALTH OUTCOME, AND PHARMACOGENOMIC ASSESSMENTS

### 6.1 Efficacy Assessment

### 6.1.1 Subject Diary

During Visit 1, a diary will be given to each subject. Subjects will be trained how to complete the diary and instructed in the use of the diary. The importance of completing the diary daily throughout the study will be stressed. The subject will complete the diary daily throughout the study until Day 42 (the End of Treatment Visit). The diary will be used to record the subject-reported variables of the CDAI,

Site personnel will assess the subject's compliance with the use of the diary throughout the study.

During the screening period, subjects must have entered sufficient diary data to allow calculation of the CDAI score (see Section 6.1.2). Subjects with poor compliance completing the diary during screening will be considered screen failures. Subjects with poor compliance completing the diary during the treatment period may be withdrawn from the study.

The data obtained from the subject diary will be used for calculation of the subject-reported variables of the CDAI and other efficacy outcomes measures such as the PRO-2,

The subject will record the following information in the subject diary to assess CD activity:

- 1. Number of liquid or very soft stools
- 2. Abdominal pain/cramps
- 3. General well-being
- 4. Fever over 100°F (37.8°C)
- 5. Use of anti-diarrheal drugs (e.g., loperamide, diphenoxylate, or opiates)

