### 4.2.5 Early Termination Visit

A subject will have an Early Termination Visit if they discontinue treatment with study drug or withdraw from the study. If a subject withdraws from the study, or is discontinued from treatment with study drug, every effort should be made to complete an Early Termination Visit with the same assessments as scheduled for Day 42. The Early Termination Visit should be scheduled as soon as possible after it has been decided that the subject will be permanently discontinued from treatment with study drug. In addition to the Early Termination Visit, the Follow-up Visit should be performed on Day 56 if possible. Details describing subject withdrawal are presented in Section 4.5.

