### 4.5 Subject Withdrawal

All subjects are free to withdraw from participation in the study at any time, for any reason, specified or unspecified, and without prejudice to further treatment. In addition, subjects will be withdrawn from study drug and from the study in the following circumstances:

- The Investigator decides that the subject should be withdrawn. If this decision is made because of an intolerable AE or a clinically significant laboratory value, the study drug is to be discontinued and appropriate measures are to be taken. The Medical Monitor is to be notified immediately.
- The subject is unwilling to continue in the study.
- Noncompliance or protocol violations that in the opinion of the Investigator or Sponsor/designee necessitates the subject being removed. The decision to withdraw the subject should be taken in consultation with the Medical Monitor.
- Pregnancy
- Events that require emergency unblinding
- Has infectious complications that require stopping or reduction of immunosuppressive therapy

- Requires any abdominal surgery or surgery for fistula or abscesses; the decision to withdraw the subject should be taken in consultation with the Medical Monitor.
- The Investigator or the Sponsor, for any reason, stops the study.

In general, before the decision is made to withdraw the subject, consultation with the Medical Monitor is recommended.

If a subject chooses to withdraw from the study (permanently stop taking the study drug), they will be encouraged to return to the site for safety reasons to complete the assessments planned for Visit 5 (Day 42) during an Early Termination Visit and for the Follow-up Visit (Day 56).

The Investigator should ensure that all reasonable attempts (telephone calls, contact with primary care physician, certified letter) are made to obtain follow-up safety information on subjects who do not return to the site for study visits or are lost to follow-up.

Subjects who are withdrawn from the study after randomisation and who receive at least one dose of study drug will not be replaced. These subjects cannot be rescreened.

Subjects who withdraw from the study after dosing should be advised by the Investigator to continue contraception restrictions for 90 days after the last administration of study drug.

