# % VHsquared

STATISTICAL ANALYSIS PLAN: PROTOCOL V56502

Page 13 of 40

- i. Inclusion criterion 2: CDAI score of ≥220 to ≤450 during Screening
- ii. Inclusion criterion 3: CRP  $\geq$ 5 mg/L (or, if CRP is normal, FCP  $\geq$ 250 µg/g) at screening.
- iii. Inclusion criterion 4: Active CD of ileum and/or colon as determined by the baseline ileocolonoscopy
- b. The following exclusion criteria should be absent in the data for the subjects:
  - i. Exclusion criterion 3: Any gastrointestinal (GI) manifestations of CD that might affect the evaluation of efficacy.
  - ii. Exclusion criterion 5: Prior primary efficacy failure of or secondary loss of response to anti-TNFα therapy, or any contraindication to anti-TNFα therapy
  - iii. Exclusion criterion 6: The use of medications prior to the study or during the study with the potential to affect the evaluation of efficacy.
- 2. Mishandling of the study drug which could have impacted the integrity of the study data such as nonallowable temperature deviations during storage or dispensing of study drug to the wrong subject
- 3. Non-compliance rate of <80% or >120% with study treatment.
- 4. Use of prohibited concomitant medications.
- 5. Study procedures done outside protocol-specified window period that are judged to affect study efficacy data.
- 6. Assessments for primary endpoint not done.

Protocol deviations will be reviewed prior to unblinding and individual subjects having protocol deviations will be evaluated for inclusion in the PP population. Any additional deviations not listed above will be documented at this time.

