### **6.3. DERIVED TIMEPOINTS**

Last observation carried forward (LOCF) method will be used for primary analysis. If any of the element (Patient reported data or Physician reported data or Haematocrit value ) of primary endpoint is missing at Day 42, LOCF will be applied and that element will be carried forward from last available post-baseline visit.

Also, LOCF will be performed as part of sensitivity analysis for the primary and secondary efficacy endpoints. The missing CDAI scores, CRP and FCP will be carried forward from the last available post-baseline measurements.

In addition, the worst observation carried forward (WOCF) will also be performed as part of sensitivity analysis for the missing CDAI scores, CRP and FCP from the available baseline, post-baseline and the unscheduled assessments.

The descriptive summaries of derived timepoints provided for the primary efficacy variables will be summarised and named as "Day 42 (LOCF)" and "Day 42 (WOCF)".

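### Withdrawing a randomised subject from the whole study for poor diary or capsule compliance replaces the observed Day 42 endpoint with an earlier value, and the missing data are avoidable

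*Protocol*

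**What the plan says.** Three protocol sections bear on non-compliance after randomisation.

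- **Protocol 6.1.1 (diary):** "Subjects with poor compliance completing the diary during the treatment period may be withdrawn from the study". The available text does not define poor compliance.
- **Protocol 5.12 (capsules):** problems such as "missing 2 or more consecutive full days [at least 6 doses] or taking less than 80% or more than 120" per cent of doses between visits "should be discussed with the Medical Monitor to determine if the subject may continue in the study". On timing: "At Day 14 and Day 42, previously dispensed study drug will be retrieved by the Investigator and compliance assessed".
- **Protocol 4.5 (withdrawal):** the circumstances that take a subject off study drug and out of the study together include "Noncompliance or protocol violations that in the opinion of the Investigator or Sponsor/designee necessitates the subject being removed", with Medical Monitor consultation. The same section treats leaving the study as permanently stopping study drug.

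After withdrawal, Protocol 4.2.5 says "every effort should be made to complete an Early Termination Visit with the same assessments as scheduled for Day 42", as soon as possible after the decision, with the Day 56 visit if possible. Under Protocol 6.1.2, a subject who stops treatment early records CDAI data only until that visit.

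On the analysis side, SAP 5.1 and 15.1.3 keep every randomised subject in the primary analysis. For a missing CDAI element at Day 42, SAP 6.3 says "LOCF will be applied and that element will be carried forward from last available post-baseline visit". SAP 6.4 summarises Early Termination data together with Day 42. SAP 5.2 lists "Non-compliance rate of <80% or >120% with study treatment" as a ground for exclusion from the per-protocol set.

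**The concern.** An ITT analysis needs a Day 42 status for every randomised subject, so compliance after randomisation should not decide whose Day 42 status is observed. Here it can. Diary and capsule compliance may plausibly track symptoms and tolerability, so values lost this way may be related to outcome, and possibly differently in the two arms.

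The loss also serves no analytic purpose. Poor capsule compliance is already dealt with in the per-protocol set, and a gap in the diary can be filled one element at a time while the rest of the Day 42 assessment is used as observed. What is at stake is how many subjects contribute a true Day 42 observation to the primary endpoint, and whether those who do not are a selected group.

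**Working it through.** **1. The plan's own figure.** The Protocol synopsis gives 126 randomised (84:42), 10% dropout and 114 completers (76:38).

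- 126 × 0.90 = 113.4; 84 × 0.90 = 75.6, rounded to 76; 42 × 0.90 = 37.8, rounded to 38; 76 + 38 = 114.
- Allowance: 126 − 114 = 12 subjects.

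The figure reproduces. The 10% is not split by reason, so the documents do not show whether compliance withdrawals are inside it. For scale, 5% of 126 is 6.3 subjects, about half the allowance.

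**2. How early the substitute value can be.** Between Day 1 and Day 42 the only scheduled visit is Day 14 (Protocol 4.2.2). If withdrawal is decided there and the Early Termination Visit follows at once, the gap is 42 − 14 = 28 days, nominally. If the problem is first seen at Day 42, the visit is already taking place and nothing is lost.

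**3. What is observed at Day 42 if assessment continues.**

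| Endpoint part | Source | Needs the diary? |
|---|---|---|
| CRP or FCP | blood or faecal sample (Protocol 6.1.3) | No |
| Haematocrit, weight, abdominal mass, complications other than fever | central laboratory and site (Protocol 6.1.2) | No |
| Stools, pain, well-being, fever, anti-diarrhoeal use | diary (Protocol 6.1.1 and 6.1.2) | Yes, the previous 7 days |

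Two things follow. A subject with a poor diary before Day 14 can still have a complete Day 42 CDAI if the last week is recorded. And because response requires both the CDAI criterion and a biomarker fall of at least 40% (SAP 15.1.1), a Day 42 biomarker that misses 40% settles non-response without any diary data.

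**4. What is observed if the subject is withdrawn at Day 14.** CDAI recording stops at the Early Termination Visit. The Day 56 visit cannot supply the diary part, because the diary runs only to Day 42. The whole composite then rests on a value from about Day 14.

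**5. Illustrative power.** The available text gives no response rates or power, so the rates here are assumptions: placebo 10/20/30/40% against V565 33.1/46.2/57.4/67.3%, chosen to give about 80% power at 76:38. Power = Φ[(|p₁ − p₂| − 1.96·SE₀)/SE₁], where SE₀ uses the pooled proportion and SE₁ the separate ones.

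*Observed Day 42 values only,* with extra withdrawals on top of the 10%:

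| Extra | Subjects with a Day 42 value | Power |
|---|---|---|
| 0% | 113.4 | 80% |
| 5% | 107.1 | 77–78% |
| 10% | 100.8 | 74–75% |
| 15% | 94.5 | 71–72% |

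*ITT (84:42) with carried-forward values.* Let m be the share with a substituted value and f the ratio of early to Day 42 response, the same in both arms. Each arm's rate becomes p × (1 − m + m·f).

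| f | m = 10% | m = 20% |
|---|---|---|
| 1 | 84% | 84% |
| 0.5 | 80–82% | 75–78% |
| 0 | 75–78% | 65–71% |

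If early response equals Day 42 response there is no power loss. If compliance withdrawals already sit inside the 10%, m stays at 10% and planned power does not change.

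**The case against.** The strongest reply is that the plan has a working fallback. A withdrawn subject is to have an Early Termination Visit with the Day 42 assessments, CDAI recording runs to that visit, missing values are carried forward (with a worst-observation sensitivity analysis in SAP 15.1.4), and ITT keeps everyone. A reader might infer that one missing diary entry costs the whole primary endpoint. The documents do not support that: the trigger is poor compliance, the wording is permissive, and the endpoint is replaced by an earlier value, not left absent.

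A reader might also infer that sites can remove subjects on their own for capsule counts. Protocol 5.12 and 4.5 both bring in the Medical Monitor, and the general wording in 4.5 could be read to cover the diary too. Only the 6.1.1 sentence lacks that step.

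It can also be said that the gain is limited. For a subject who keeps a poor diary throughout, much of the Day 42 CDAI will still be carried forward, and if nothing usable was recorded after baseline there is nothing to carry. This stands as a limit on the benefit, but the biomarker and the site-assessed items would still be observed at Day 42.

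Finally, a rule giving every subject who stops drug a Day 42 visit would cover most of this. That is true provided it names non-compliance explicitly; otherwise 4.5 still ends participation. The detailed LOCF criteria and the Schedule of Events are not in the available text, so the exact effect on responder status cannot be traced.

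**Conclusion.** The point holds as one of avoidable, possibly outcome-related missing data in the primary endpoint. Non-compliance can end assessment as well as treatment, and the observed Day 42 result then gives way to one up to about 28 days earlier, although the SAP's element-level carry-forward and per-protocol exclusion make that unnecessary.

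Its size cannot be derived from the documents. The power ranges above rest on assumed response rates, an assumed number of extra withdrawals and an assumed relation between early and Day 42 response; they run from no loss upwards. A reader might try to fix the bias by counting all withdrawn subjects as non-responders with unequal withdrawal by arm. The SAP does not plan that rule for the primary analysis, the documents give no withdrawal split, and the direction of the bias would depend on which arm lost more subjects. No stated figure in the plan is wrong. This is an inexpensive improvement to data collection and does not show that the trial is underpowered or the result invalid.

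**What to change.** The change concerns data collection only.

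- **Protocol 6.1.1:** state that poor diary completion leads to retraining and does not by itself end scheduled assessments. Define poor diary compliance.
- **Protocol 5.12 and the noncompliance item in 4.5:** state that non-compliance does not by itself end assessments, and that subjects who agree keep the Day 42 and Day 56 assessments.
- **Protocol 6.1.2:** for these subjects, continue CDAI diary recording to Day 42.
- **SAP 5.2:** continue to classify capsule non-compliance through the per-protocol set. Say in the SAP whether an Early Termination value counts as Day 42 in the responder analysis or enters only through LOCF.

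Protocol 4.2.5, 4.5, 5.12, 6.1.1 and 6.1.2 must be reconciled on whether leaving study drug also ends assessments. Any decision about study drug stays as the protocol has it.

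The cost is a short amendment across these sections, with no new type of visit or procedure; some subjects who would have left attend the existing Day 42 visit. The downside is that some Day 42 CDAI scores will contain carried-forward diary elements. For a subject with no usable diary data after baseline, only CRP/FCP and the site-assessed items will be observed.

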### 6.1.2 Crohn's Disease Activity Index

Crohn's Disease Activity Index (CDAI) is the most commonly used measure of clinical activity in patients with CD [12, 13, 14]. Some of the data used to calculate the CDAI is obtained from the subject diary (see Section 6.1.1) and some is obtained at site visits. The CDAI will be calculated at the time points identified in .

The CDAI consists of eight variables:

- 1. Total number of liquid or very soft stools (total for previous 7 days)
- 2. Abdominal pain/cramps rating (total for previous 7 days)

- 3. Subjective general well-being rating (total for previous 7 days)
- 4. Total number of listed categories the subject has experienced during the last 7 days (Note: all of these are assessed by the Investigator with the exception of fever, which is obtained from the subject diary.)
  - a. Arthritis or arthralgias
  - b. Iritis/uveitis, erythema nodosum, or pyoderma gangrenosum
  - c. Aphthous ulcers
  - d. Anal fissures, fistulae, or abscess
  - e. Other fistula (specified by site personnel)
  - f. Fever higher than 100°F or 37.8°C during previous week
- 5. Use of anti-diarrheal drugs (e.g., loperamide, diphenoxylate, or opiates)
- 6. Presence of abdominal mass
- 7. Anaemia based on haematocrit (HCT) value entered into formula:
  - a. For men = 47 HCT value
  - b. For women = 42 HCT value
- 8. Body weight in kilograms (kg) entered into formula:
  - a. ([standard weight in kg actual weight kg] / [standard weight in kg]) x 100%

The responses are scored numerically and weighted. Total CDAI scores range from 0 to approximately 600 points; a higher score indicates a more active disease. A CDAI score of <150 points denotes remission, a score between 150 to 219 points denotes mildly active disease, a score of  $\geq$ 220 to  $\leq$ 450 points denotes moderately active disease, and a score of >450 points denotes severe disease.

During the study, the CDAI will be calculated from the scores obtained from the subject-reported variables of the CDAI and the results recorded at the site. Haematocrit values will be extracted from the central laboratory results and used for the calculation of the CDAI score.

Subjects who prematurely discontinue treatment prior to Day 42 will be asked to continue to record CDAI data until the Early Termination Visit.

Instructions for recording the CDAI score will be given at Visit 1 (see Section 6.1.1). Data should be reviewed at each study visit, including unscheduled visits.

A sample of a CDAI score worksheet is provided in the Appendix (Section 12.1)

### 6.1.3 Biomarkers of Inflammation

The collection of CRP and/or FCP will occur at the time points indicated in .

C-reactive protein is an acute-phase reactant produced in the liver and is an easily measured non-specific marker of inflammation. It is a widely used marker of inflammation in CD and elevations in CRP have been associated with endoscopic inflammation in CD [15, 16].

C-reactive protein will be analysed in blood samples. If CRP values are normal, FCP will be assessed in the faecal samples. FCP will be used as the eligibility test if CRP results are <5 mg/L. During the treatment and follow up phase of the study, FCP will only be evaluated in subjects whose screening CRP was <5 mg/L, and who qualified for the study based on their screening FCP value.

Calprotectin is abundant in the cytosol of activated neutrophils. The amount of FCP is directly proportional to neutrophil influx into the intestinal tract and is a reliable non-specific marker of intestinal inflammation [17, 18, 19]. While currently endoscopy with biopsy is considered the gold standard for evaluating the extent and location of inflammatory mucosal lesions, studies have shown that FCP may also be a useful marker of intestinal inflammation.

On Day 1, the faecal sample for FCP should be collected prior to administration of the first dose of study drug. The subject may also provide a sample from faeces passed one day prior to the scheduled visits. These samples will be collected in sterile containers (to be provided to the subjects) and refrigerated at home. At each sampling time point, approximately 2 g to 5 g of faeces will be collected.

# 6.1.4 Abdominal Pain and Stool Frequency Instrument (PRO-2)

PRO-2 will be calculated at the time points indicated in .

The PRO-2 is a composite score that measures abdominal pain and soft stool frequency averaged over seven days [20]. The data for the total PRO-2 score is extracted from selected subject-reported variables of the CDAI included in the subject diary. These data are the entries for the number of liquid or soft stools/day and abdominal pain (rated on a scale of 0-3) assessed over the course of seven days.

### 6.1.5 Ileocolonoscopy

It is important to confirm that subjects are eligible for the ileocolonoscopy prior to Visit 2. During the screening period, subjects must have entered sufficient diary data to allow calculation of the CDAI score, have CDAI scores  $\geq 220$  to  $\leq 450$  and CRP level  $\geq 5$  mg/L [or if CRP is normal, FCP level  $\geq 250 \ \mu g/g$ ]). The timing of the Visit 2 is flexible but the ileocolonoscopy must not be done until it has been documented that the subject is eligible for the ileocolonoscopy.

It should be noted that subjects who have had an ileocolonoscopy within 12 weeks of Visit 1 do not require an ileocolonoscopy at Visit 2 *provided it is forwarded to the central reader and was performed in such a way as to enable evaluation by the central reader.* 

Video images of all endoscopic procedures will be captured and sent to a qualified central reader.

The images will be examined to determine the central reader's overall impression of the state of mucosa to assess eligibility for randomisation and to calculate the SES-CD (see

VHsquared Ltd Protocol V56502 Drug Name: V565

Section 6.1.6). Active disease must be confirmed by the central reader in order for the subject to proceed to Visit 3 and randomisation on Day 1.

